The strength of using national databases is that they will capture any event of aneurysm rupture irrespective where it occurs in the UK. Rupture is a sudden severe event that always results in a hospital admission or death and it is not anticipated that there is a significant rate of SAH undiagnosed in the community. Rupture could not be identified from the neurosciences records however as many patients who suffer rupture of their aneurysm will be admitted to another hospital (e.g. their local hospital is not a neurosciences centre, or they have moved home, etc). These databases are also linked to ONS and so can capture causes of death for patients who die before reaching hospital. The comprehensive coverage offered by these admission databases will recreate the high follow-up rates that are normally only achieved with a prospective study.

In the third stage local neurosurgery units will confirm the admissions identified in stage 2 were correctly coded as a subarachnoid haemorrhage. This will be a final quality control to mitigate for any issues with miscoding in HES/PEDW/SMR to and ensure the data derived is accurate and meaningful.

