- Population: European/North American, Finnish, Japanese (where race cannot be confirmed it will be assumed to be non-Finnish and non-Japanese on the basis that there is a low incidence of these populations in the UK and their presence would usually be considered noteworthy in a clinical note.

The additional desirable covariates at time of diagnosis will include:

- aspirin use any dose used >3* per week
- statin use any statin use >3* per week
- smoking history non-smoker, ex-smoker, current smoker
- Aneurysm multiplicity record number of intra-dural aneurysms the patient has (treated or untreated)
- Family history number of 1 first degree and second degree relatives with UIA/SAH
- History of Autosomal Dominant Polycystic Kidney Disease yes, no
- Aneurysm location subclassification ICA paraclinoid (ophthalmic and superior hypophyseal) ICA (PCom), ICA other (anterior choroidal and bifurcation), ACA ACOM, ACA pericallosal, MCA, Posterior (basilar termination), Posterior (SCA), Posterior (AICA) Posterior (PICA)
- Bleb or irregularity of aneurysm recorded as present or absent from radiology report only. If not mentioned in report assumed to be absent. If no radiology report available, then recorded as NA.
- New/known diagnosis: patients in whom the aneurysm was known prior to the search period will be recorded as known diagnosis and otherwise as new diagnosis.

Data collection – aneurysm rupture/censoring events – local neurosciences units

At the time of baseline data collection locally available follow up will be recorded which will include:

• Date of last follow-up

- Date of death (if applicable)
- Cause of death (if applicable)
- Date of SAH (if applicable)
- Location of aneurysm causing SAH (if applicable)
- Date of aneurysm treatment (if applicable)
- Reason for aneurysm treatment (if applicable)

This data will be used for quality control of subsequent HES searches.

Data collection - aneurysm rupture/censoring events - central HES ONS data

Upon collection of all baseline data, a search of the Hospital Episode Statistics (HES) and Office for National Statistics (ONS) databases using the patient's NHS numbers be conducted. The use of a HES and ONS search is designed to maximise the identification of rupture events which are not treated in neurosurgical unit as subarachnoid haemorrhage. It will thus identify events managed in a district general hospital or those who die pre-hospital.

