This search will use ICD-10 codes as defined by the UK biobank Outcome Adjudication Group (Definitions of Stroke for UK Biobank Phase 1 Outcomes Adjudication Date: August 2017 Version: 1.1 https://biobank.ndph.ox.ac.uk/showcase/showcase/docs/alg_outcome_stroke.pdf). This will identify the following events:

- 1. Admission to hospital with aneurysmal subarachnoid haemorrhage (I60.0-I60.7)
- 2. Occlusive treatment of aneurysm.
- 3. Death diagnosed as subarachnoid haemorrhage in parts 1a-c of the death certificate.

All patients identified from the HES search with any of the above events will then have their medical notes re-evaluated by the local neurosurgery unit to confirm the HES report has accurately identified the event as aneurysm rupture or treatment.

A similar search will be repeated in Wales using NWIS/PEDW where NHS numbers are also used. Scotland does not use NHS numbers making searches more complex. However, a further search of equivalent database (SMR01) will be performed in Scotland using name and date of birth for identification.

Data collection - quality assurance - central HES ONS data

Additionally, all patients will be checked for possible SAH events that could have been miscoded.

Therefore, any patients with the codes:

- 1. Subarachnoid haemorrhage (other and unspecified) (I60.8-60.9)
- 2. Intracerebral haemorrhage (including intraventricular haemorrhage (I61.0-61.9)
- 3. Non-traumatic subdural haemorrhage (I62.00-I62.02)
- 4. Traumatic subarachnoid haemorrhage (S06.6X0, S06.6X9A, S06.6X9, S06.6X8A)

will have their casenotes reviewed for evidence the haemorrhage was aneurysmal.

Any patients with the following codes:

- 5. I46.1 sudden cardiac death
- 6. R96 other sudden death cause unknown
- 7. R98 unattended death

will have their casenotes reviewed to assess if their death was likely due rupture of their aneurysm.

Additionally, in at least one pilot site, all patients with the code

8. Cerebral infarction (63.0-63.9 & I64.X)

will have their casenotes reviewed to estimate rates of missed diagnosis for the whole cohort.

Where verification cannot be established from medical notes, any patients with codes in the specified possible miscoded SAH events will be assumed to be non-aneurysmal unless they have a procedure code indicating occlusive treatment of aneurysm within 30 days after the event, or they were coded as

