7.1.2 Exclusion criteria

- 1. Mycotic or vasculitic aneurysms.
- 2. Aneurysm diagnosed on CT or MRI alone.
- 3. AVM associated flow aneurysms.
- 4. Extradural aneurysms (e.g. intra-cavernous).
- 5. Aneurysms previously treated by either microsurgical or endovascular techniques.
- 6. Small lesions uncertain as to whether they are truly aneurysmal ("dilatation", "bulge", 'Infundibulum", etc)

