8.4 Patient & Public Involvement

University Hospitals Southampton has run focus groups to identify research priorities for patients with unruptured aneurysms and with subarachnoid haemorrhage since 2012. These focus groups have been drawn together by advertising at meetings of the Wessex SAH support group and on Facebook and email with previous patients. [name], the Chief investigator, also has experience of working with the James Lind Alliance, who represent the gold standard in patient and public involvement, through his membership of the Stroke Association Steering Committee for the Stroke Priority Setting Partnership.

This study has developed from multiple meetings with the Wessex Subarachnoid Haemorrhage Support Group to prioritise research questions for patients with SAH and UIA. The support group is a forum for patients and carers with SAH and UIA established in 2001 and available to over 2000 patients during that time. It runs bimonthly meetings with typically 30 to 50 participants and has been on Facebook since 2016 (187 current members). Recurrently the main themes at Q&A are around anxiety, and more specifically "what is the risk I will have a haemorrhage". Anxiety over the risk of rupture of unruptured aneurysms is routinely cited as the greatest concern for both patients with

unruptured aneurysms (and patients who have suffered subarachnoid haemorrhage and had one aneurysm treated but have further untreated unruptured aneurysms). It is also a major concern for relatives and carers who fear losing loved ones. These observations of patient concerns were mirrored closely in an analysis of online discussion groups of patients with UIA.

The majority of patients are advised not to undergo treatment based on our existing understanding of the condition, however, knowledge of the presence of their aneurysm and uncertainty as to exactly what risk it poses and whether it should be treated can have devastating effects on people's lives who frequently describe an inability to move on or enjoy life again. Conversely in patients undergoing treatment of their aneurysms there is huge concern whether they are making the right decision to undergo a procedure with risk of death or major disability when we don't know exactly what risk their aneurysm poses. There is therefore huge support for further studies of unruptured aneurysm risk and most are amazed to hear how most of our decisions are based on disputed data from Finland and Japan.

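### Verification of linked events does not tie a rupture or treatment to the included, untreated aneurysm, so a later bleed from another aneurysm would be confirmed as an outcome

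*Protocol*

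**What the plan says.** Protocol section 5 (central HES ONS data) searches by patient for three events: admission with aneurysmal SAH, "Occlusive treatment of aneurysm", and death certified as SAH. Patients with a hit have their notes re-evaluated "to confirm the HES report has accurately identified the event as aneurysm rupture or treatment". Section 3 describes the same stage: "local neurosurgery units will confirm the admissions identified in stage 2 were correctly coded as a subarachnoid haemorrhage". For haemorrhage codes that may be miscoded SAH, section 5 says patients "will have their casenotes reviewed for evidence the haemorrhage was aneurysmal".

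On eligibility, section 7.1.2 excludes "Aneurysms previously treated by either microsurgical or endovascular techniques". That removes the treated aneurysm, not a patient who has another, untreated one. Previous aneurysmal SAH is a core covariate in section 5. Multiplicity is an additional covariate and counts treated as well as untreated aneurysms. Section 8.4 recognises "patients who have suffered subarachnoid haemorrhage and had one aneurysm treated but have further untreated unruptured aneurysms" as a patient group.

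The location of the aneurysm that bled is a field in the local follow-up, recorded at baseline data collection and described as quality control for the later HES search. For treatments, the local fields are date and reason, without location. Under Aim 1, section 5 expects no significant overestimation, and hence no correction for it, because all SAH events are verified in the notes.

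**The concern.** The study is meant to describe the natural history of unruptured aneurysms. Site, size and irregularity describe a particular aneurysm, but the outcome is found through the patient's identifiers and confirmed only as a true aneurysmal SAH or a true treatment. In a patient with more than one aneurysm, these need not refer to the same lesion.

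The misattribution would not be spread evenly. It can arise only in patients who have or had another aneurysm, many of whom have a previous SAH. Previous SAH is one of the PHASES items to be validated under Aim 1, and multiplicity is a candidate predictor under Aim 2. False events there would raise the apparent effect of both predictors and the observed risk in the PHASES categories that hold these patients. All planned corrections deal with underestimation, so none is designed to detect this error.

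**Working it through.** This is mainly a check of the text. Take a patient with aneurysm A, which bled or was treated, and aneurysm B, which is untreated and included.

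1. **Re-bleed from A after inclusion of B.** The admission carries an SAH code. The notes confirm an aneurysmal SAH, and the review question in sections 3 and 5 is satisfied. Nothing asks whether B bled. The event is a confirmed rupture for a record holding B's site and size. This follows directly from the wording.

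2. **SAH from A that led to the discovery of B.** Inclusion is dated from the first angiogram in the search period, which may be the one done for that SAH. The first admission then falls at or before time zero. Later-dated episodes or transfers for the same bleed are true SAH and could be returned by the search, which states no onset limit. Counting them is permitted, not ordered.

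3. **Occlusion of A shortly afterwards.** The search and review accept occlusive treatment without naming the aneurysm. It could be taken as the end of follow-up for B. The censoring rule's own wording points to the included aneurysm but does not define it.

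4. **Fallback when notes cannot settle a possibly miscoded event.** An occlusion code within 30 days makes the event aneurysmal. Occlusion of A meets this as well as occlusion of B.

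5. **Can the location field catch these?** It is filled in at baseline data collection, before linkage. Events found only by linkage, which are the reason for linking, have no such entry. Nor is location made a condition for counting an event.

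**Figures.** The protocol gives no share of events from other aneurysms. Its planning figures reproduce:

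- Rate: 51 / (1,692 × 4.1) = 51 / 6,937.2 = 0.00735 per person-year.
- Patients for 60 events: 60 / (51 / 1,692) = 1,990.6 (stated 1,990).
- Person-years for 60 events: 60 / 0.0073517 = 8,161.4 (stated 8,161).

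Suppose a share s of 60 confirmed ruptures came from another aneurysm. Then 60 × (1 − s) are true outcomes, and the rate is overstated by 1 / (1 − s). The values of s are assumptions.

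| s | True outcomes among 60 | Overstatement |
|---|---|---|
| 5% | 57 | 1.05 |
| 10% | 54 | 1.11 |
| 20% | 48 | 1.25 |
| 30% | 42 | 1.43 |

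**The case against.** The strongest reply is that the protocol already leans towards the included aneurysm. Previous SAH has its own place as a baseline covariate. Under Aim 1, the local notes are to supply SAH events that come after baseline, and HES is compared over a similar period. Under Aim 3, time is measured from diagnosis. The censoring rule speaks of the aneurysm in the singular, and the review of sudden-death codes asks about rupture of the patient's own aneurysm. Local neurosurgical teams read the notes and would often recognise a presenting bleed. A separate data definitions manual, not shown, may contain an attribution rule.

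Much of this stands for the presenting SAH and for censoring. A reader might infer that the protocol orders a presenting SAH to be counted, or that occlusion of the ruptured aneurysm removes these patients from follow-up within days. The text supports neither as a stated rule. For Aim 1 the statistical paragraph does not even list treatment among its censoring reasons.

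It does not answer the later re-bleed from a treated aneurysm, which occurs after inclusion and passes every stated check.

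Aim 1 also adjusts total risk for differences between local and HES events. That could offset part of an inflated overall rate. It cannot identify the source of events known only from linkage, and it does not correct hazard ratios.

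**Conclusion.** The point holds as a gap in the outcome definition. Verification establishes that an event was an aneurysmal SAH or an aneurysm treatment. It does not establish that the included, untreated aneurysm was involved or that onset followed inclusion. A later re-bleed from another, treated aneurysm is therefore a confirmed rupture as written. Misuse of later episodes of a presenting SAH, or of occlusion of the aneurysm that bled, is possible, but the wording leans against it. The statement that note verification rules out significant overestimation is not supported on this point.

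The direction for false events is clear: upward, and concentrated in patients with previous SAH or multiple aneurysms. The size is unknown. It is tempting to assume what fraction of patients enter through an SAH from another aneurysm and what fraction of those bleeds are miscounted, and so to quote a number of false events. The protocol gives neither fraction, so such a number would reflect only the assumptions. The 1.05- to 1.43-fold range is likewise illustration, not an estimate.

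Should fix, with moderate confidence, because the unseen manual may already carry a rule.

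**What to change.** - In section 3 (third stage) and section 5 (central HES ONS data), require the note review to record, for every linked event, which aneurysm ruptured or was treated. This extends the existing local location field to linked ruptures and adds it for treatments.
- Count as an outcome a rupture of an included, untreated aneurysm with onset after the date of inclusion. Do not count events that the notes attribute to another aneurysm.
- Treat SAH and occlusion codes from the admission in which the aneurysm was found, including transfers, as baseline information.
- State in the last-follow-up rule in section 5 that censoring at treatment means treatment of the included aneurysm.
- Keep events of undetermined source in the primary analysis as a stated exception to the counting rule, and exclude them in a sensitivity analysis.
- Put the same rule in the data definitions manual.

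The cost is wording plus one or two fields at a review already planned for these events. The downside is that some events will have no determinable source. The sensitivity analysis will show how much they matter.

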There are multiple potential causes leading to underestimates of rupture risk. The magnitude of these will be estimated and corrected for. In view that all SAH events will be verified in clinical notes it is not expected that there will be any significant overestimation and consequently correction. Events may be missed due to migration. Any patients noted at time of baseline data collection to have emigrated will have this recorded and this will be used for censoring. Additionally, HES data will reveal any patients who have unregistered with their GP for emigration which will be used as a censoring event. Unfortunately, it is anticipated that not all patients will unregister on departure from the UK and therefore the observed emigration rate (that from the baseline data collection and HES data) will be subtracted from average national migration figures and this applied to the data.

Events may be missed due to miscoding. Aneurysmal SAH miscoded as:

1. Cerebral infarction (63.0-63.9 & I64.X)

Will be identified at one or more test sites by review of clinical notes to estimate any under-estimates due to miscoding and these estimates applied to the whole cohort.

In the event there are high rates of failed verification for the codes:

- 1. Intracerebral haemorrhage (including intraventricular haemorrhage (I61.0-61.9)
- 2. Subarachnoid haemorrhage (other and unspecified) (I60.8-60.9)
- 3. Non-traumatic subdural haemorrhage (I62.00-I62.02)
- 4. Traumatic subarachnoid haemorrhage (S06.6X0, S06.6X9A, S06.6X9, S06.6X8A)
- 5. I46.1 sudden cardiac death R98 unattended death
- 6. R96 other sudden death cause unknown
- 7. R98 unattended death

at some centres, then error estimates may be applied to the data from centres with robust code verification.

Additionally, at baseline data collection, any subsequent SAH events observed in the local notes will be recorded with their date, or date of last follow up. The SAH events observed during this follow up period will be compared to that for the similar period using HES data (after applying the above corrections), and the total risk estimates adjusted for any differences between these to give final 5 year risk estimates.

Discrimination will be assessed with the C statistic but is expected to be poor due to low event rates and therefore will be compared to the original PHASES data. Calibration will be assessed with calibration plots and Hosmer-Lemeshow tests.

Statistical analysis – Aim 2 - Additional prognostic factors

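### The traumatic SAH entry in the miscoding check is incomplete in any single code format, and the subdural entry lacks its parent code

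*Protocol*

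**What the plan says.** Protocol section 5 describes the main outcome search thus: "This search will use ICD-10 codes as defined by the UK biobank Outcome Adjudication Group". It looks for I60.0 to I60.7, occlusive aneurysm treatment, and SAH in part 1 of the death certificate.

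A second search follows under the heading Data collection - quality assurance - central HES ONS data. It is meant to pick up ruptures filed under another diagnosis. Patients with a listed haemorrhage code "will have their casenotes reviewed for evidence the haemorrhage was aneurysmal". The four haemorrhage entries are:

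- "Subarachnoid haemorrhage (other and unspecified) (I60.8-60.9"
- "Intracerebral haemorrhage (including intraventricular haemorrhage (I61.0-61.9"
- "Non-traumatic subdural haemorrhage (I62.00-I62.02"
- "Traumatic subarachnoid haemorrhage (S06.6X0, S06.6X9A, S06.6X9, S06.6X8A"

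The same four entries appear again under Statistical analysis - Aim 1 - PHASES validation, in the paragraph that begins "In the event there are high rates of failed verification for the codes". Neither place gives a prefix, truncation or all-subcodes rule. The protocol does not state how many characters HES, PEDW or SMR01 hold.

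**The concern.** The code list decides who is reviewed. A patient whose record does not match it is not looked at by this route, and without another trigger stays event-free or is censored at death.

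The first two entries are complete four-character ranges. The traumatic SAH entry is four separate strings that follow no visible pattern: ending 9 appears with and without the suffix A, ending 0 only without it, ending 8 only with it, and endings 1 to 7 not at all. The subdural entry is a proper range, but one character longer than its parent I62.0, which is not listed.

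The protocol lists these codes because it regards them as possible miscoded ruptures; collapse with a head injury is one plausible route. It also names underestimation as the main threat to its risk estimates and expects no material overestimation to offset it. Missed records would therefore push the UK rupture risk down, in the quantity to be compared with PHASES.

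**Working it through.** The protocol states no miscoding share and no capture rate for these codes, so there is no figure of its own to reproduce. Two checks are possible.

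**1. Exact match of the listed strings**

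The listed S06.6 strings are X0 and X9 (6 characters) and X8A and X9A (7 characters). The three storage formats below are assumptions.

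| Assumed format | Possible strings | Listed strings that match | Match by stem S06.6 |
|---|---|---|---|
| 4-character, S06.6 | 1 | 0 | 1 of 1 |
| 6-character, X0 to X9 | 10 | 2 (X0, X9) | 10 of 10 |
| 7-character, X0A to X9A | 10 | 2 (X8A, X9A) | 10 of 10 |

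For subdural haemorrhage, a record stored as I62.0 matches none of I62.00, I62.01 and I62.02. A record stored as one of those three does match. The stem I62.0 catches both forms.

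These are counts of code strings. The share of patients behind each string is unknown.

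**2. Scale of the possible loss**

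Missed events = events x share of ruptures coded only this way x share of those missed. The share coded this way is assumed to be 0.5% to 5%, and the share missed 0% to 100%. Neither comes from the protocol. At 100% missed:

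- Aim 1 target of 60 events (section 7.2.1): 60 x 0.005 = 0.3 and 60 x 0.05 = 3.0.
- Aim 2 target of 120 events: 120 x 0.005 = 0.6 and 120 x 0.05 = 6.0.
- Full follow-up of 113,905 years: the protocol's source rate is 51/(1,692 x 4.1) = 0.735% per year, giving about 837 ruptures. Then 837 x 0.005 = 4.2 and 837 x 0.05 = 42.

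The relative bias cannot exceed the assumed share. At 0.735% per year the five-year risk is about 5 x 0.735 = 3.7%, so a 5% loss is about 0.18 percentage points. All of these are upper limits, before any other route recovers a patient. At 0% missed, every figure is zero.

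**The case against.** **Matching may not be literal.** If the extract is matched on the parent code or truncated to it, nothing is lost. A reader might infer that the search misses most such records. The document does not support that as a fact: it states neither the storage format nor the matching rule, and strings are not records. What stands is that the written list is incomplete in every single format tested.

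**The format is not uniquely odd.** A reader might say these two entries differ from all the others. They do not: the list also has three-character R96 and R98, and "Cerebral infarction (63.0-63.9 & I64.X" lacks its letter in the range and uses a filler X. Nor is the subdural entry a handful of picked codes; it is a range without its parent.

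**Other routes exist.** The same patient may be found through another I60 code or an I61 code, through aneurysm treatment, or through SAH on the death certificate. An unverified case with a traumatic SAH or subdural code counts as a rupture only if the aneurysm was treated within 30 days, and the treatment search finds that patient anyway. The Aim 1 section also compares SAH events in local notes with HES over a similar period and adjusts the risk for the difference. This objection largely stands, and it shrinks the loss.

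It does not remove it. Section 3 says rupture cannot be identified from neurosciences records, because many patients are admitted elsewhere, so the local comparison is weakest where the national search matters most. That comparison also adjusts total five-year risk and does not put individual events back into the models for Aims 2 and 3. The correction for failed verification concerns codes that were returned but not confirmed, so it cannot reach records never selected.

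**Conclusion.** The point holds as a defect in a stated rule. The traumatic SAH entry is incomplete in any one format, the subdural entry lacks its parent, and both are repeated in the Aim 1 section. If the list is matched literally, the ruptures at risk are those coded only under S06.6 or I62.0, not treated, not certified as SAH and managed outside the neurosciences unit.

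The bias would be downward and is probably small. Its size cannot be determined from the document. A reader might take the figure of up to 42 lost ruptures as an estimate. It is not one: it needs the full 113,905 years, an assumed 5% share, total loss under literal matching, and no recovery by any other route.

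**What to change.** In both places, replace the two entries with the parent categories and all their subcodes: any code beginning S06.6, and any code beginning I62.0. State that matching is by stem in HES, PEDW and SMR01, and leave the casenote review as planned. The subdural stem should be I62.0; searching on the whole of I62 would go beyond the subdural category that the protocol names.

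The cost is two edited lines in each of two places and a few more casenotes. The edit should be made before the data request. If that has already gone out, the list of codes actually matched should be checked and the correction made for the planned repeat searches.

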subarachnoid haemorrhage other or unspecified and they subsequently died within 30 days (based on the very low rate of mortality from non-aneurysmal SAH) and did not have any additional codes for trauma indicating a non-aneurysmal event.

Data collection - other considerations - central HES ONS data

Last follow-up for each patient will be set as the time at which the HES search was performed, or the patient was unregistered with a GP in the UK or date of death, or the aneurysm was treated, whichever is earliest.

Additionally, we will record

- 1. race
- 2. I10 essential (primary) hypertension
- 3. Z72.0 tobacco use
- 4. F17.2 tobacco dependence

And use these to complete any missing baseline data. Where baseline data and HES conflict, the baseline data will be used. Where neither is available, after assessment for any bias (missing completely at random MCAR, missing at random MAR, missing not at random MNAR) multiple imputation will be used.

Statistical analysis - Aim 1 - PHASES validation

The PHASES study provides the coefficients from their Cox regression model and baseline survival at 5 years that allows the absolute 5-year risk of rupture, to be calculated for all patients who are not censored before 5 years, using age, whether the patients has hypertension, history of SAH, size of aneurysm (3 categories) and location of aneurysm. The time to censoring will be calculated (death or date of HES search or date unregistered from GP practice whichever is first) to ensure 5 years of follow up if rupture has not occurred. Discrimination will be assessed using Harrell's C-index of concordance and Royston and Sauerbrei's D statistic. Calibration will be assessed at the 5 year time point using the method in Royston (2014). These will be used to calculate the number of SAH events per 5 years for each PHASES score (0 to 12+) and expressed as a percentage with 95% confidence interval to compare to the PHASES estimates.

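### The rupture endpoint does not exclude bleeding caused by aneurysm treatment, and the 30-day procedure rule can count some of it as natural-history rupture

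*Protocol*

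**What the plan says.** All of this is in Protocol section 5 unless stated.

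- **Primary search** (*aneurysm rupture/censoring events - central HES ONS data*). Admissions coded I60.0-I60.7, occlusive treatments and deaths certified as SAH go back to the local unit "to confirm the HES report has accurately identified the event as aneurysm rupture or treatment".
- **Possible miscoding** (*quality assurance - central HES ONS data*). Patients coded I60.8-60.9, I61, I62.0 or S06.6 "will have their casenotes reviewed for evidence the haemorrhage was aneurysmal".
- **Default when notes do not settle it** (same subsection). Bleeds on that list which review leaves unresolved do not count as aneurysmal. The exception that matters here reads "unless they have a procedure code indicating occlusive treatment of aneurysm within 30 days after the event". A second exception covers other or unspecified SAH followed by death within 30 days without trauma codes.
- **End of follow-up** (*other considerations - central HES ONS data*). The earliest of several dates: the HES search, GP deregistration, "or date of death, or the aneurysm was treated, whichever is earliest".
- **Aim 1 censoring**. The list is "death or date of HES search or date unregistered from GP practice whichever is first". Treatment is not on it.
- **Aim 3**. Patients whose aneurysm was occluded are kept in a time-to-event analysis over all available follow-up.
- **Overestimation** (Aim 1). Because events are to be verified in notes, "it is not expected that there will be any significant overestimation and consequently correction".
- **Local data**. Each unit records the SAH date, treatment date and reason for treatment, for quality control of the HES search.

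**The concern.** Section 2 of the Protocol says that management rests on weighing treatment risk against natural history. A bleed provoked by clipping or coiling is a treatment risk. If it enters the endpoint as a rupture, it moves to the other side of that balance.

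The error would not be spread evenly. It can arise only in patients selected for treatment, so it would follow whatever features drive that selection. It could distort PHASES calibration (Aim 1), the coefficients of the new model (Aim 2) and the long-term rates (Aim 3).

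The 30-day rule is sensible when a bleed leads to treatment. It points the wrong way when treatment led to the bleed, and nothing in its wording separates the two.

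**Working it through.** **1. Following a procedural bleed through the rules**

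Take an elective treatment admission in which the aneurysm bleeds during or soon after the procedure. Section 3 describes the linked data as admissions with the diagnoses coded during each, and section 5 defines the main event as an admission. No text says whether an event is dated at admission, at onset or at the procedure, or how same-day ties are resolved.

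- *Notes found.* The aneurysm did rupture and the haemorrhage was aneurysmal, so either review question can be answered yes. Neither asks about cause.
- *Notes not decisive, code on the possible-miscoding list, event dated at admission.* The procedure falls on or after the event date and within 30 days, so the rule can accept the bleed as rupture.
- *Same, event dated at true onset.* The procedure came first or on the same day. If first, the rule does not accept the bleed; if the same day, the text does not decide.
- *Bleed after a first procedure, second occlusive procedure within 30 days.* The rule accepts it, unless follow-up was already cut at the first procedure.

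**2. Does ending follow-up at treatment close these routes?**

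Applied consistently, it removes any bleed dated after treatment. It does not remove one dated to the start of the admission. The Aim 1 list read literally does not apply the cut-off at all, and the Aim 3 sentence can be read as following patients past occlusion.

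**3. Rupture rate, checked against the plan's own sample size (section 7.2.1)**

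- Rate = 51 / (1,692 × 4.1) = 0.735% per year.
- Years for 10 ADPKD events = 10 / 0.007352 = 1,360 (stated 1,360).
- Total years = 1,360.2 × 4,436 / 53 = 113,849 (stated 113,905).
- Patients at 5 years each = 22,770 (stated 22,781).

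The plan's figure reproduces and is not in dispute. The rate is used below.

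**4. Expected true ruptures at 22,781 patients**

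- At 5 years each: 113,905 × 0.007352 = 837.
- At the pilot projection of 132,200 / 31,130 = 4.25 years each: 96,744 × 0.007352 = 711.

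**5. Illustrative inflation**

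False events = patients × share treated × procedural bleeding risk × share of such bleeds counted.

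The 32% treated is borrowed from the ISUIA crossover figure in section 1. The 1% bleeding risk is an assumption: section 1 gives only a combined permanent morbidity or mortality risk of 5% or more.

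| Share counted | False events | Against 837 | Against 711 |
|---|---|---|---|
| 10% | 22,781 × 0.32 × 0.01 × 0.1 = 7.3 | +0.9% | +1.0% |
| 100% | 22,781 × 0.32 × 0.01 = 72.9 | +8.7% | +10.3% |

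Wider assumptions (10% to 50% treated, 0.5% to 3% bleeding, 10% to 100% counted) give 1 to 342 false events, or +0.1% to +41% of 837. At a rupture rate of 1% per year (1,139 true ruptures) the range is +0.1% to +30%.

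**The case against.** The strongest reply is that nothing in the Protocol says these bleeds are counted. Follow-up ends at treatment, a procedural bleed happens during or after treatment, and the 30-day rule needs the procedure to come after the event. The rule is also narrow: it covers only the possible-miscoding codes, not I60.0-I60.7, and only where notes do not settle the matter. Notes for an elective treatment admission should usually be available. Units record the treatment date and reason, which would identify an elective case. A separate data definitions manual, not shown, may say more.

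Much of this stands:

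- A reader might infer that every procedural bleed is counted. The text does not support that, because event dating is unspecified.
- A reader might infer that verification looks only for rupture. The primary review covers rupture or treatment.
- A reader might infer that no downward correction is possible. Aim 1 adjusts the total risk estimates for differences between local and HES SAH counts, in either direction. It would not, however, catch a procedural bleed that local notes also record as SAH.
- A reader might multiply 15% to 32% treated by 1% to 3% bleeding, obtain 34 to 219 false events and quote 5% to 31% of 711. That range rests on outside assumptions and on every such bleed being counted.

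The gap remains. Note review, where it works, still does not ask about cause. The recorded reason for treatment is not used by any rule to reject an event. The cut-off at treatment is stated in one place and missing from the Aim 1 list. The Protocol introduces the manual in connection with case-note data collection, and it could not by itself reconcile conflicting censoring text in the Protocol.

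**Conclusion.** The point holds in a limited form. The plan does not exclude periprocedural haemorrhage from the rupture endpoint, and its stated rules, followed literally, can count some of it. This is more than missing detail, because one rule takes any later occlusive treatment as evidence of rupture whatever its purpose.

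The expectation of no significant overestimation is therefore not secured. Its premise is that all SAH events are verified in notes, yet the quality-assurance subsection provides for events that cannot be. Verification as worded would not remove procedural bleeds in any case.

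The documents cannot settle the size. It depends mainly on the share of procedural bleeds that gets through, which is unknown. The figures of about 1% and about 9% to 10% are scenarios at 32% treated and 1% bleeding, not estimates.

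**What to change.** 1. Define the endpoint as spontaneous rupture before any occlusive treatment.
2. Add a spontaneous/procedural item to the planned note review, using the treatment date and reason already collected.
3. State how events are dated and how a bleed and a procedure in the same admission are handled.
4. Let the 30-day rule confirm rupture only when the haemorrhage was the reason for the admission or the treatment. An emergency-admission marker could serve, if the English, Welsh and Scottish linked data carry one; the Protocol does not say.
5. Censor haemorrhage first coded in an elective treatment admission at the treatment date, and tabulate it separately.
6. Reconcile censoring at treatment between the general follow-up rule, the Aim 1 list and the Aim 3 analysis set.
7. Add a sensitivity analysis that leaves out events accepted only through the 30-day rule.

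The cost is a few sentences in the Protocol, one item in a review already planned, one extra table and one extra analysis. The downside is a slightly lower event count.
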